3.4 Blinding of Study Product

Given the nature of the application of the wound closure device, which will be visible to the surgeon at the time of application and the patient postoperatively, the study will not be blinded to either the surgeon or the patient. Prior to discharge, a blinded plastic surgeon will be asked to assess the wound based on comessis and overall quality of wound healing.

4 Study Procedures

Patients who are eligible for the study will be notified on a preoperative visit via a tool on the electronic medical record system (Epic).

At this time, surgeon research assistant will ask the patient if they would like to be involved in the study. If consent to participate in the study is given, the surgeon will go ahead with the randomization process, which will dictate what type of wound closure device will be used at the time of the surgery. All of the wound devices are currently being used at the institution. The study will follow normal standard of care for the application of these devices. The only different will be the randomization process that will take place prior to the surgery. Data will be collected regarding the primary outcomes at the time of discharge as well as at their normally scheduled postoperative visits. Patients will be followed up to their 3rd postoperative visit. Prior to discharge, a plastic surgeon, who will be blinded to the type of wound closure technique that the patient received, will assess the wound for the quality of wound healing. At their postoperative visits, the physician will document whether a complication had occurred. Patients will also be given patient-reported outcome questionnaires, including VAS scores and HWES, that will measure the level of satisfaction of their wound healing at the time of these visits.

The following table shows the visits and procedures/ observational data collection that will occur during the study:

Activity	Pre-operative assessment	Date of surgery	Prior to discharge	Postop visit #1	Postop visit #2	Postop visit #3
Study team procedures						
Consent	X					
Medical History	X			X	X	X
Physical Exam	X		X	X	X	X
Height	X			X	X	X
Weight	X			X	X	X
Vitals signs	X		X	X	X	X
Record of			X	X	X	X

CONFIDENTIAL

This material is the property of the NYU School of Medicine and Langone Medical Center. Do not disclose or use except as authorized in writing by the study sponsor

complications						
Perioperative costs – cost of supplies, time to wound closure, operative times, length of stay, readmissions		X	X			
Randomization		X				
Study treatment dispensation		X				
Subject Survey – VAS score, HWES score			X	X	X	X

5 Statistical Plan

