3.2 Method for Assigning Subjects to Treatment Groups

Names of patients who are consented for the study will be inputted into a computer and randomized to one of the three treatment groups based on an alternating method. A randomized control trial will provide the highest level of evidence without altering the potential risks to the patient as all three wound closure techniques have been found to have comparable complication rates.

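### The Section 4 text reads as the surgeon randomising at the preoperative consent visit, but the visit table puts randomisation on the day of surgery; the plan should fix one time point and take assignment out of the surgeon's hands

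*Combined protocol and SAP*

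**What the plan says.** **Section 4, text.** Eligible patients are notified at a preoperative visit, and at that point they are asked whether they want to take part. Then, if consent is given, "the surgeon will go ahead with the randomization process, which will dictate what type of wound closure device will be used". Later in the same paragraph: "The only different will be the randomization process that will take place prior to the surgery".

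**Section 4, visit table.** Consent is marked under the preoperative assessment. The row "Randomization" has a single mark, under the date of surgery, in the same column as dispensation of the study treatment.

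**Section 3.2.** Consented patients are entered into a computer and "randomized to one of the three treatment groups based on an alternating method". No time point and no concealment step is given.

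**Section 2.6.** Participating surgeons identify candidates and discuss the study with them. Research assistants explain it and obtain written consent.

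**Section 3.4.** Neither surgeon nor patient is blinded. A blinded plastic surgeon assesses the wound before discharge. At later visits, under Section 4, the physician records complications and is not said to be blinded.

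**The concern.** Text and table cannot both be followed when the consent visit and the operation fall on different days. The difference matters because of who acts and what that person knows. Under the text, the surgeon who chose and counselled the patient also performs the assignment, is unblinded, and holds the result until the operation.

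Three risks follow:

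- **Selective entry.** A surgeon who can foresee the next arm can influence who is offered the trial.
- **Arm-dependent handling.** Operative time and time to wound closure are collected and feed the cost objective. Both depend on the surgeon, who would know the closure before the operation starts.
- **Losses after assignment.** A patient who cancels or withdraws between assignment and surgery has no wound outcome. Sections 5.1 and 5.2 name no analysis population, no dropout allowance, and no rule for patients randomised but not operated on or closed with another device.

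**Working it through.** **Step 1: the timing statements side by side (all in Section 4).**

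| Place | Time of randomisation | Who |
|---|---|---|
| Text, consent sentence | Follows consent at the preoperative visit; no date given | Surgeon |
| Text, later sentence | Before surgery | Not stated |
| Visit table | Date of surgery | Not stated |

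The consent sentence points to the visit and the table to the day of surgery. The later sentence fits either, so it does not settle the matter, and Section 3.2 is silent. The conflict lies between the natural reading of one sentence and an explicit table entry.

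**Step 2: what depends on the time point and what does not.** The interval between assignment and surgery exists only if assignment takes place at the visit. Foreseeing the next arm is a separate matter. If alternating means a fixed rotation through three arms, anyone who sees the last assignment knows the next one, at the visit or on the day of surgery. Moving the time point therefore shortens the window for loss and early knowledge but leaves predictability untouched. Both need a remedy.

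**Step 3: can the size be computed?** The plan's recruitment figures (Section 5.1) are:

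- 700 × 0.50 = 350 approached
- 350 × 0.60 = 210 expected to follow through
- 210 − 200 = 10 above target

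The total of 200 cannot be reproduced, because neither event rates nor a significance level is stated. No cancellation rate and no visit-to-surgery interval is given. The size of the risk therefore cannot be derived from the documents.

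**Step 4: an illustration of precision only.** Assume complication rates of 20% and 4% and a two-sided 0.05 level for one pairwise comparison, with n = 200/3 = 66.7 per arm. None of the rates or the level comes from the plan. Power is Φ(z), with p̄ = 0.12 and

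z = [0.16 − 1.96·√(2·p̄·(1 − p̄)/n)] / √[(0.20·0.80 + 0.04·0.96)/n]

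| Assumed loss | n per arm | z | Power |
|---|---|---|---|
| 0% | 66.7 | (0.16 − 1.96 × 0.0563)/0.0546 = 0.91 | 0.82 |
| 5% | 63.3 | (0.16 − 1.96 × 0.0577)/0.0560 = 0.84 | 0.80 |
| 10% | 60.0 | (0.16 − 1.96 × 0.0593)/0.0575 = 0.76 | 0.78 |

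Under these assumptions the loss of precision is modest. The more serious question is whether losses differ by arm, and nothing in the documents lets one estimate that.

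**The case against.** **The text never says that randomisation happens at the visit.** The time reference attaches to the research assistant's question, and the next sentence is conditional and undated. Consent at the visit with assignment on the morning of surgery fits every statement. This stands in part: the conflict is inferred from the natural reading of the sentence. But staff working from the text alone would most likely randomise at once, and nothing tells them to wait.

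**A reader might infer that the patient learns the arm before surgery and then cancels or asks to switch.** The documents do not say so. Section 3.4 explains the open label by the closure being visible to the surgeon when applied and to the patient afterwards. Nothing delays disclosure, so it is possible, but it is not stated.

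**A reader might infer that 10 to 20 patients would be lost, using up the whole margin of 10.** That takes 5% to 10% of 200, and the rate is conjecture. The 210 is a recruitment forecast, not a cap, and the 60% who follow through may already allow for withdrawals before surgery.

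**A reader might also infer that randomisation loses its protection.** That would need losses, entry or handling that in fact depend on the arm. Losses unrelated to arm cost precision only.

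**Timing is not the main weakness, because alternation is predictable whenever it is done.** This stands, and it is why a change of date alone is not enough.

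**Conclusion.** The point holds as an inconsistency at a step where bias can enter. The Section 4 text most naturally has the surgeon randomise at the preoperative visit; the table says the day of surgery. Followed as written, the text lets an unblinded, recruiting surgeon run and know an unconcealed alternating allocation before the operation. The consequences are risks, not documented events, and their size cannot be computed from the plan.

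The conclusion rests on two readings: that the consent sentence describes one continuous step at the visit, and that the absence of any concealment wording means none is planned. It does not rest on any assumed cancellation rate or on early disclosure to the patient. Correction is worthwhile because the remedy is cheap and the table already points to it.

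**What to change.** 1. Rewrite the Section 4 text to match the table: consent at the preoperative visit, randomisation once, on the day of surgery, before the operation.
2. In Sections 3.2 and 4, have a research assistant, not the surgeon, obtain the assignment from a concealed computer-generated random sequence that replaces the alternating method. State who may see the assignment and when.
3. In Section 5.2, state that patients are analysed as randomised, and say how those randomised but not operated on, or closed with another device, are handled and reported.

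**Cost.** Items 1 and 3 are wording. Item 2 needs a sequence to be set up and a research assistant available on operating days. All three closures must be available on the day; Section 3.3 says all are in use at the institution, which is not the same as being stocked in every operating room. Delaying assignment until shortly before skin closure would narrow the window further, but it is optional and goes beyond what the table requires.

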A single-center, phase IV, randomized, prospective study investigating the efficacy of various wound closure devices in reducing postoperative wound complications

Regulatory Sponsor: **[name]**

Co-Investigators: [name]
[name]

NYULMC Orthopaedic Surgery
Hospital of Joint Diseases
[name]
[name]

Study Product: Zipper wound closure device, Monocryl + Dermabond,
Polyester mesh + Dermabond

Protocol Number: s16-02020

NCT Number: NCT03134209

Version: 1/10/17

CONFIDENTIAL

This material is the property of the NYU School of Medicine and Langone Medical Center. Do not disclose or use except as authorized in writing by the study sponsor

Initial version: 12/15/16

List of Abbreviations

TJA- Total joint arthroplasty

CONFIDENTIAL

This material is the property of the NYU School of Medicine and Langone Medical Center. Do not disclose or use except as
authorized in writing by the study sponsor

Study Summary

Title	A single-center, phase IV, randomized, prospective study investigating the efficacy of various wound closure devices in reducing postoperative wound complications
Short Title	Assessing various wound closure techniques; RCT
Protocol Number	i16-02020
Phase	4
Methodology	Randomized, control
Study Duration	7 months
Study Center(s)	Single-center
Objectives	To determine the efficacy of the experimental wound closure device in regards to reducing wound complications and costs
Number of Subjects	200 subjects
Diagnosis and Main Inclusion Criteria	Patients who are undergoing joint arthroplasty
Study Product, Dose, Route, Regimen	Zipper surgical skin closure device applied to the most superficial layer of skin following a joint arthroplasty
Duration of administration	Applied one-time to close the wound following joint arthroplasty. This device will be applied for up to 2-3 weeks
Reference therapy	Experimental treatment will be compared to two groups: 1) Monocryl + Dermabond 2) Polyester mesh + Dermabond
Statistical Methodology	Odd ratios will be used to determine which wound closure device is at higher risk of developing a wound complication

CONFIDENTIAL

This material is the property of the NYU School of Medicine and Langone Medical Center. Do not disclose or use except as authorized in writing by the study sponsor

Introduction

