3.3 Preparation and Administration of Study Product

The three different treatment devices will be administered following the normal standard of care. All three wound closure devices are currently being used at NYULMC. No modifications to the normal standard of practice other than the randomization process will be implemented.

CONFIDENTIAL

This material is the property of the NYU School of Medicine and Langone Medical Center. Do not disclose or use except as authorized in writing by the study sponsor

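### The pre-discharge wound rating is called blinded, but no masking is described and the zipper is probably still on the skin when the wound is rated

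*Combined protocol and SAP*

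**What the plan says.** The rating appears twice. Section 3.4 (Blinding of Study Product) states: "Prior to discharge, a blinded plastic surgeon will be asked to assess the wound based on comessis and overall quality of wound healing". Section 4 (Study Procedures) repeats it: "Prior to discharge, a plastic surgeon, who will be blinded to the type of wound closure technique that the patient received", and has this surgeon judge the quality of healing.

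Section 3.4 also explains why the rest of the trial is open. It describes the closure device as one "which will be visible to the surgeon at the time of application and the patient postoperatively" and concludes that "the study will not be blinded to either the surgeon or the patient".

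The Study Summary gives the position and duration of the experimental device: "Zipper surgical skin closure device applied to the most superficial layer of skin following a joint arthroplasty", and "This device will be applied for up to 2-3 weeks".

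No section describes a covering, removal before rating, coded photographs, a delayed rating or any other way to keep the rater from seeing the closure. The visit table in section 4 has no row for this rating. Sections 2.2 and 2.3 do not list it as a primary or secondary endpoint. Section 5.2 does not name it; it refers only in general terms to perioperative outcomes.

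**The concern.** Section 3.4 gives up blinding of the patient because the device can be seen after surgery. Its next sentence calls a surgeon who inspects the same wound blinded. Withholding the allocation from that surgeon does not help if the allocation can be read from the skin.

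At stake is what may be claimed for this rating. It is the only assessment that the protocol calls blinded, in a trial otherwise open to surgeon and patient. The hypothesis at the end of section 1.1 sets the zipper against the other two techniques, so recognition of the zipper alone would unmask both comparisons of interest. A judgement of cosmesis and healing is subjective, and a reader would give it more weight if told that it was blinded.

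**Working it through.** The plan gives no figure to reproduce. The check sets the sections side by side and compares two times.

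**Inputs**
- Zipper wear, W: a maximum of 2-3 weeks, so 14 to 21 days (Study Summary).
- Zipper position: the skin surface (Study Summary).
- Time of rating: before discharge (sections 3.4 and 4).
- Day of discharge, D: not given. Length of stay is only collected as data (visit table).
- Masking method: none found in any section.
- Mesh: self-adhesive and combined with a topical adhesive (section 1.1); wear time not given.

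**Step 1: is the zipper on the skin at the rating?** Wear remaining at discharge is W − D, and the device is off only if D is at least W. Take D from 1 to 7 days as an assumption, with the device worn for its full stated time:
- shortest remaining wear: 14 − 7 = 7 days;
- longest remaining wear: 21 − 1 = 20 days.

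The device is in place throughout that range. For a device worn its full stated time, the result reverses only if discharge falls on or after day 14 to 21. Because the stated wear is a maximum, earlier removal is not strictly excluded, so the finding is likely rather than certain.

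**Step 2: can the rater see it?** The protocol itself says that the device is visible to the patient postoperatively. A surgeon examining the wound has at least the same view unless something prevents it, and nothing of that kind is described.

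**Step 3: what is unmasked?** Three arms give 3 × 2 / 2 = 3 pairwise comparisons. Two of them involve the zipper (against Monocryl + Dermabond and against mesh + Dermabond). If only the zipper is recognised, those two are unmasked. If the mesh is recognised as well, the remaining arm follows by elimination and all three are. The documents do not settle whether the mesh is recognisable at discharge.

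**Step 4: what depends on the rating?** No listed endpoint, sample-size figure or named analysis does.

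**The case against.** The strongest reply is that the protocol is silent on masking rather than opposed to it. A method may simply be unwritten, and for an unlisted outcome this is a minor clarification.

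Part of that stands. A reader might infer that masking is ruled out, because section 3.3 says "No modifications to the normal standard of practice other than the randomization process will be implemented" and section 4 says "The only different will be the randomization process that will take place prior to the surgery". In context both sentences concern how the devices are applied. Section 4 goes on to add study assessments, including this rating and the questionnaires. The sentences therefore do not exclude a masking step.

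Three other stronger readings also go beyond the documents:
- That covering the closure would necessarily hide the wound. Nothing shows how much of the incision the device covers.
- That a bias can be sized by counting how often a rater could name the arm. Such counts restate the assumption that the device is recognised and measure no distortion of the rating.
- That the complications are known to be recorded by people aware of the arm. Section 4 has the physician document them at postoperative visits, and does not say whether that person knows the arm. This is a separate matter from the rating.

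What does not stand is that silence makes the label harmless. The plan asserts that the rater is blinded, and its own statements on visibility and wear time point the other way. If it is followed as written, the likely result is an unmasked rating reported as a blinded one.

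**Conclusion.** The point holds for the rating and no further: the blinding stated in sections 3.4 and 4 is not supported by the design as described. Provided that discharge precedes zipper removal, at least the zipper arm is visible to the rater, two of three pairwise comparisons are unmasked, and the rating cannot be reported as blinded. If all closure material were off before discharge, the problem would not arise.

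The size and direction of any bias cannot be estimated from the documents. A reader might infer that the primary result is compromised. It is not on this ground, because the rating is neither a primary nor a secondary endpoint and the complication analysis does not use it. The change should be made because the claim is wrong as written and cheap to correct; the trial's main comparison does not turn on it.

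**What to change.** Choose one of the following, and bring sections 3.4 and 4 and the visit table into line, with a row for the rating.

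**(a) Move the rating.** The same assessor rates the wound once, at a named and already scheduled postoperative visit after all closure material is off the skin, in person or from coded photographs. The sponsor must choose the visit: the documents give neither visit dates nor mesh wear time. Costs:
- the rating then measures later rather than early healing, so it is a different outcome;
- patients who miss that visit have no rating;
- the assessor's availability at that visit is not stated, and up to 200 patients would need to be seen or photographed;
- residual skin marks might still hint at the technique.

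No extra visit is needed.

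**(b) Keep the pre-discharge rating.** Stop calling it blinded unless a workable masking method is written into the protocol, and report it as unblinded. Without a masking method this costs only wording, and it keeps the early measurement.

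Neither option changes how long any device is worn.

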Wound closure techniques have been well-studied in a variety of surgical specialties, however, the level of evidence reported in the literature in regards to TJA is scarce. Thus, the current randomized, control trial study aims to investigate the perioperative outcomes and costs of various wound closure techniques including zipper technology, monocryl suture plus Dermabond, and polyester plus Dermabond wound closure techniques. The zipper wound technology is a new wound closure device that is an alternative to the commonly used conventional staples and sutures. The device acts like a scaffold to stabilize the adjacent sides of a wound in order to minimize forces that can disrupt normal healing of the skin. Monocryl suture plus Dermabond is a commonly used combination of wound closure techniques today. Finally, the polyester plus Dermabond closure techniques combines the OCA topical skin adhesive with a flexible, self-adhesive polyester mesh that has proven to reduce wound closure times and have a significant greater skin holding strength than skin staples or subcuticular sutures in one study. Although there have been prior studies measuring the efficacy of these closure techniques individually, none have compared these three particular ones following TJA. Furthermore, in order to provide the highest level of evidence as possible for the study, it will be conducted in a randomized fashion.

CONFIDENTIAL

This material is the property of the NYU School of Medicine and Langone Medical Center. Do not disclose or use except as authorized in writing by the study sponsor

The hypothesis of the study is that there will be reduced complications rates, improved outcomes, and overall cost reduction for the zipper technology versus the other two closure techniques.

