2.1 General Design

A single-center, phase IV, randomized, prospective study. Patients will be expected to participate for about 4 months. Please refer to section 4 for a summary description of the sequence and duration of all trial periods including follow-up.

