2.3 Secondary Study Endpoints

Cost effectiveness will be determined by the increased LOS, readmissions, cost of supplies, and differences in wound closure time between the differences in wound closure techniques. Each of these variables will be calculated based on the associated hospital costs and analyzed to determine the most cost effective wound closure technique.

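### The cost comparison records the time taken to close the wound but nothing about taking the closure material off, and this may favour the zipper.

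*Combined protocol and SAP*

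**What the plan says.** The Study Summary gives a wear time for the zipper: "This device will be applied for up to 2-3 weeks". It gives none for the two comparators.

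The schedule table in section 4 has one row for costs and times, listing supply costs and "time to wound closure, operative times, length of stay, readmissions". It is marked in the surgery-day and pre-discharge columns and is blank at all three postoperative visits. The treatment row, "Study treatment dispensation", is marked on the day of surgery only. No row records removal of closure material.

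Follow-up continues well beyond the wear time. Section 4 states: "Patients will be followed up to their 3rd postoperative visit". Section 2.1 states: "Patients will be expected to participate for about 4 months".

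Cost is defined in three places:
- Section 1.4 uses supplies, length of operation and postoperative complications.
- Section 2.3 says: "Cost effectiveness will be determined by the increased LOS, readmissions, cost of supplies, and differences in wound closure time".
- Section 5.2 repeats the items of 2.3, worded as examples rather than as a closed list.

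Sections 2.3 and 5.2 then promise to identify the technique with the best cost-effectiveness. The hypothesis in section 1.1 is "reduced complications rates, improved outcomes, and overall cost reduction for the zipper technology versus the other two closure techniques".

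**The concern.** Closure methods can differ in the work needed to apply them and in the work needed to take them off. The plan collects the first and has no place for the second. If the zipper is quicker to apply but needs a later removal step that a comparator does not, the comparison credits the saving and omits the offsetting cost. That error would be systematic, so a larger sample would not reduce it.

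Closure time also carries much of the comparison. Section 10.2 says supply costs do not differ between the techniques, so supplies should not separate the arms. Section 1.3 reports that earlier trials found similar complication rates for the zipper and sutures, but faster closure with the zipper. Closure time is therefore a component on which the protocol's own evidence points to a zipper advantage, and it is the one measured on one side only.

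**Working it through.** The plan states no figure on this point, so there is nothing to reproduce. The check is mainly a comparison of passages.

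**1. Does removal fall outside the measured window?** The wear time is up to 2-3 weeks (Study Summary). The last mark in the cost row is before discharge (section 4). The documents give no expected length of stay. That removal comes after discharge is therefore an inference, resting on the assumption that patients go home before the device comes off.

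**2. Is removal captured elsewhere?**

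| Place | Application counted as | Removal counted |
|---|---|---|
| 1.4 | length of operation | no |
| 2.3 | wound closure time | no |
| 5.2 | wound closure time | not named; list left open |
| Section 4, cost row | closure and operative time | no |
| Section 4, other rows | treatment given, day of surgery | no |

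The open list in 5.2 would permit a removal item, but no planned data collection would supply it. Complications are recorded to visit #3 and enter cost under 1.4, but a routine removal is not a complication.

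**3. Which way does it lean?** Against Monocryl + Dermabond, the zipper is expected to be faster to close (1.3 cites a comparison with conventional sutures). If suture and glue need less removal work, which the protocol does not address, the omission favours the zipper. Against the mesh, section 1.1 describes that technique too as reducing closure time, and its removal is equally undescribed. No direction can be assigned.

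**4. Could it matter in size?** The documents give no minutes and no unit costs, so the actual size cannot be computed. The following illustration uses assumed values throughout and assumes no removal work in the comparator arm. Per zipper patient:

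net saving = s × o − (r × c + v)

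- s = closure minutes saved: 2, 5, 10
- o = theatre cost units per minute: 20, 40, 80
- r = removal minutes: 2, 5, 10
- c = clinic cost units per minute: 2, 5
- v = cost of a separate visit: 0, 50, 150

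This gives 3 × 3 × 3 × 2 × 3 = 162 combinations.

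- Lowest: 2 × 20 − (10 × 5 + 150) = 40 − 200 = −160.
- Highest: 10 × 80 − (2 × 2 + 0) = 800 − 4 = +796.
- Negative in 29 of 162, and not negative in 162 − 29 = 133.

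Split by v, 54 combinations each, the negatives number 1 (v = 0), 7 (v = 50) and 21 (v = 150); 1 + 7 + 21 = 29. The single case with no visit cost is 2 × 20 − 10 × 5 = −10. So on these values removal minutes alone hardly ever reverse a saving; a separate visit can. The counts describe the chosen grid and are not probabilities.

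**The case against.** The strongest objection is that no passage describes zipper removal. A device that comes off after some weeks need not generate a staff step: the patient may take it off, or it may be removed at one of the three routine postoperative visits that all arms attend. The extra cost would then be a few minutes or nothing. This stands. It limits the claim to a possible bias of unknown size, but the trial as planned could not show that the cost is negligible.

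A reader might infer that every zipper patient incurs an uncounted staff cost. The documents support only that the device is worn for a limited time. A reader might also infer that all cost data stop at discharge. That is true of the cost row but not of the whole plan, because complications recorded to visit #3 count under 1.4.

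It can also be said that the row is labelled perioperative and that 2.3 and 5.2 value items at hospital cost, so leaving out outpatient removal is a choice of costing perspective. That is arguable, but the plan does not state such a perspective, and the row already lists readmissions, which by nature follow discharge. Extending the row to later visits for readmissions would correct part of the same row, but removal would remain unrecorded unless it is named.

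**Conclusion.** The point holds in a limited form. As written, the secondary cost comparison measures the application side of closure time and collects nothing on removal in any arm. This may favour the zipper, most plausibly against Monocryl + Dermabond; against the mesh the direction is unknown. The size cannot be derived from the documents and could be small or zero.

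The conclusion rests on one inference, that the zipper comes off after discharge. The lean against Monocryl + Dermabond further assumes that this comparator needs less removal work.

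It would go too far to infer that the omission could by itself produce the hypothesised cost reduction. Length of stay, readmissions and complications also enter the comparison, and the sign changes only in a minority of the assumed scenarios, nearly all of which include a separate removal visit. The change is still worth making: the trial intends to name a technique on cost-effectiveness, staff minutes not recorded at the time may not be recoverable later, and the visits at which to record them already exist. The primary endpoint is not affected.

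**What to change.** Add one line to the section 4 schedule and the CRF, marked at postoperative visits #1, #2 and #3 in all three arms: closure-material removal, with date, staff minutes, whether the patient did it, and whether an extra visit was made. Enter 0 where nothing was removed or no staff time was used, and keep this distinct from the not-done code in section 7.4, so that zero and missing are not confused.

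Add removal time and any removal visit, valued at hospital cost, to the cost components in 1.4, 2.3 and 5.2, and align the three lists so that they define the same endpoint. Changing only 2.3 and 5.2 would leave 1.4 in disagreement.

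Do not change how or when devices are removed; the change concerns recording only. It costs one CRF line at visits that already take place and a short text edit in three sections. The downside is that any cost advantage of the zipper may look smaller.
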